## 2.3 Blinding and Unblinding

Not applicable. This is an open-label study.

## 2.4 Protocol Amendments

All protocol amendments related to the SCLC cohort are included below.

Amendments 1-5 did not affect the statistical analysis.

Amendment 07 is to update pharmacogenetics blood sample to include all current and future tumor types.

Amendment 08 is to add nivolumab 3 mg/kg in combination with ipilimumab 1 mg/kg to the dose levels being investigated in study CA209-032, and to add an optional external evaluation of CT or MRI scans.

Amendment 09 includes:

- SCLC: arms nivolumab 3 mg/kg and nivolumab 1 mg/kg combined with ipilimumab 3 mg/kg, increase sample size.
- Updates to Blinded Independent Central Review (BICR) information.
- Allowing brain radiation prior to crossover.
- Allowing retreatment upon PD for patients with long lasting PR or CR and who had treatment held by investigator.
- For the combination arm, subjects who meet discontinuation criteria will be allowed to continue with nivolumab treatment should the study related toxicities be attributed to ipilimumab. Ipilimumab would be discontinued.
- Updates to Primary, Secondary ██████████ Objectives.
- Updates to Discontinuation criteria to include Grade 4 lymphocytopenia.
- Updates to EQ-5D collection.

Amendment 10 includes:

- Clarification regarding PK/immunogenicity sampling and pregnancy test was added.
- Safety assessments in all indications and treatment cohorts is harmonized: D4 W2 and W5 safety assessments are deleted from the NI cohorts consistent with nivolumab monotherapy.
- For options of treatment beyond progression and crossover to NI combination arm, specification of unequivocal disease progression based on non-target lesions only is added.
- Specification of response to platinum-based therapy in SCLC is added to appendices.
- For SCLC expansion cohort, clarification of stratified randomization is added.
- For subjects from NI combination who undergo a re-exposure if they achieved an initial objective response (PR or CR) or stable disease of > 3 months and had a subsequent documented progression, an option to continue treatment with nivolumab monotherapy if ipilimumab treatment was sopped due to toxicity is added.

Amendment 11 includes:

- Clarification regarding the local lab assessment timing was added.
- For SCLC expansion cohort, exact language regarding number of prior treatment lines added for consistency with Section 3.1.5 of the protocol and the study synopsis.
- Specification of the crossover option: this option refers only to the original cohorts and not the new cohorts enrolled under or after Amendment 09 implementation.
- To increase flexibility in obtainment of tumor samples, for subjects with only one site of measurable disease tumor sampling criteria for biopsies from NOT the only site of measurable disease were widened.
- Clarification regarding requirement for baseline CT and MRI brain scans.

Amendment 12:

- Changed the primary objective for the expansion SCLC cohort to require evaluation by BICR.
- Removed the limitation of enrolling subjects with 1 or 2 prior lines of therapy in the same fixed proportion of 50% for each subgroup.
- Added permission to use palliative radiation therapy to other non-target lesions.
- Added permission to use surgical resection or stereotactic radiotherapy following initial response or long-term stable disease.
- Limited PK and immunogenicity samples collection up to 2 years.
- Updated Appendix 2 of protocol (Management Algorithms) to reflect updates in the nivolumab IB.
- Updated Appendix 6 of protocol (Methods of Contraception) to reflect updates in the nivolumab IB.

Amendments 13-16 were not related to the SCLC cohort.

### **3 OBJECTIVES**

Only objectives pertinent to the SCLC Expansion Cohort will be covered in this SAP. Other objectives are covered in a separate statistical analysis plan.

#### **3.1 Primary**

##### SCLC Expansion Cohort:

- To compare the objective response rate (ORR) as assessed by a Blinded Independent Central Review (BICR) for nivolumab monotherapy versus nivolumab combined with ipilimumab (nivolumab 1 mg/kg + ipilimumab 3 mg/kg).

### 3.2 Secondary

- To assess the safety of nivolumab monotherapy or nivolumab combined with ipilimumab in subjects with advanced or metastatic SCLC.
- To assess overall survival (OS), OS rate, progression-free survival (PFS), PFS rate, and duration of response (DOR) for subjects treated with nivolumab monotherapy or nivolumab combined with ipilimumab in subjects with advanced or metastatic SCLC. PFS and DOR will be assessed by a Blinded Independent Central Review (BICR).

[REDACTED]

## 4 ENDPOINTS

### 4.1 Primary

#### 4.1.1 Objective Response Rate

The primary endpoint is the objective response rate (ORR). The ORR is defined as the number of subjects with a best overall response (BOR) of complete response (CR) or partial response (PR) divided by the number of treated subjects. The BOR is defined as the best response designation, as determined by the investigator or BICR, recorded between the date of treatment assignment and the date of objectively documented progression per RECIST 1.1 or the start date of subsequent anti-cancer therapy, whichever occurs first. CR or PR determinations included in the BOR assessment must be confirmed by a second scan no less than 4 weeks after the criteria for response are first met. For subjects without documented progression or subsequent therapy, all available response designations will contribute to the BOR assessment. For subjects who continue treatment beyond progression, the BOR should be determined based on response designations recorded up to the time of the initial RECIST 1.1-defined progression.

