## 5 SAMPLE SIZE AND POWER

### Sample size determination for SCLC expansion cohort

In Amendment 09, in addition to the original two-stage design of SCLC subjects, additional SCLC expansion cohort subjects will be randomized in a 3:2 ratio to one of 2 expansion groups: Arm A (150 subjects, nivolumab mono) or Arm B (100 subjects, nivolumab 1 mg/kg + ipilimumab 3 mg/kg) and will be stratified for number of prior treatment lines (1 vs 2 prior chemotherapy regimens).

Based on SCLC data so far observed in this study with an ORR of about 10% for nivolumab monotherapy and about 23% for nivolumab / ipilimumab combination therapy, sample sizes of  $N = 150$  for nivolumab monotherapy and  $N = 100$  for nivolumab / ipilimumab combination therapy (nivolumab 1 mg/kg + ipilimumab 3 mg/kg) will target a Type I error rate of 5% (two-sided) and will have 78% power to detect the difference between these two arms, if the true ORR rates are 10% and 23%, respectively.

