### **6.2 Treatment Regimens**

The treatment group “**as assigned**” will be retrieved from the IVRS system.

The treatment group “**as treated**” will be the same as the arm as assigned by IVRS. However, if a subject received the incorrect drug for **the entire period** of treatment the subject’s treatment group will be defined as the incorrect drug the subject actually received.

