### **6.3 Populations for Analyses**

As noted previously, this SAP describes analyses for the SCLC expansion cohort as well as the SCLC pooled pre-expansion and expansion cohorts; therefore, for the descriptions provided below, “subjects” refers to “subjects with SCLC - Expansion Cohort” and “subjects with SCLC” where applicable.

- All Enrolled Subjects: All subjects who signed an informed consent form and were registered into the IVRS.
- All Randomized Subjects: All subjects who were randomized to any treatment arm in the SCLC Expansion Cohort.
- All Treated Subjects: All subjects who received at least one dose of any study medication.
- All Response Evaluable Subjects: A subject will be part of the response evaluable subject if the following criteria are met:
  - a) BOR is in (CR, PR, PD or SD),
  - b) at least one target lesion identified at baseline,
  - c) at least one on-study timepoint with target lesion assessment (non missing percent change from baseline).
- All PK Subjects: All assigned subjects with available serum time-concentration data.
- All Immunogenicity Subjects: All treated subjects with baseline and at least 1 post baseline immunogenicity assessment.
- All PD-L1 Tested Subjects: All subjects who had a tumor tissue sample available for assessment of PD-L1 expression at baseline.
- All Treated, PD-L1 Tested Subjects: All PD-L1 tested subjects who received at least one dose of study treatment.
- PD-L1 Evaluable Subjects: All treated, PD-L1 tested subjects with quantifiable PD-L1 expression.

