## 7 STATISTICAL ANALYSES

### 7.1 General Methods

Unless otherwise noted, analyses outlined in [Sections 7.2](#) through [7.5](#) and [Section 7.9](#) will be performed using the SCLC expansion cohort treated with nivolumab monotherapy or with nivolumab in combination with ipilimumab (nivolumab 1 mg/kg + ipilimumab 3 mg/kg). Safety will be summarized for all treated subjects in the SCLC pooled pre-expansion and expansion cohorts, by treatment group (nivolumab and nivolumab 1 mg/kg + ipilimumab 3 mg/kg). All listings will be produced for the SCLC pooled pre-expansion and expansion cohorts.

The following subsections describe tabulations of discrete variables, by the frequency and proportion of subjects falling into each category, for the SCLC expansion cohort. Percentages given in these tables will be rounded and, therefore, may not always sum to 100%. Continuous variables will be summarized for the expansion cohort using the mean, standard deviation, median, minimum and maximum values.

Time to event distributions (i.e. overall survival, progression free survival, time to response, and duration of response) will be estimated using Kaplan Meier techniques. When appropriate, the

median along with 95% CI will be provided using Brookmeyer and Crowley methodology (using the log-log transformation for construction of confidence intervals). Rates at fixed timepoints (e.g. OS at 12 months) will be derived from the Kaplan Meier estimate along with their corresponding log-log transformed 95% confidence intervals. Confidence intervals for binomial proportions will be derived using the Clopper-Pearson method.

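### SCLC expansion: the randomised primary ORR comparison counts only treated subjects, leaves the grouping unstated, and no ORR analysis uses the defined All Randomized population

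*SAP*

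**What the plan says.** All references are to the SCLC expansion SAP unless stated.

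- **Objective and test.** Section 3.1 makes the primary objective a comparison of BICR-assessed ORR between monotherapy and the combination. Section 7.5.1.1 tests it with a two-sided CMH test stratified by prior treatment lines as recorded in IVRS, and adds an odds ratio and an ORR difference.
- **Design.** Sections 2.2 and 5 randomise 150 and 100 subjects in a 3:2 ratio, stratified by prior lines. Section 2.3 states that the study is open-label.
- **Denominator.** Section 4.1.1 defines ORR as subjects with a complete or "partial response (PR) divided by the number of treated subjects". Section 7.1 says that the analyses in 7.2 to 7.5 and 7.9 "will be performed using the SCLC expansion cohort treated with nivolumab monotherapy or with nivolumab in combination with ipilimumab". Section 7.5 itself names only the expansion cohort.
- **Randomised population.** Section 6.3 defines "All Randomized Subjects: All subjects who were randomized to any treatment arm in the SCLC Expansion Cohort". The only analysis assigned to it is the disposition table in 7.3.1 of subjects randomised but not treated. The ORR sensitivity analyses in 7.5.1.2 vary confirmation of response and the handling of subsequent therapy or crossover, not the population.
- **Grouping.** Section 6.2 defines both an as-assigned group (from IVRS) and an as-treated group. Under the latter, a subject given the wrong drug for the whole treatment period "will be defined as the incorrect drug the subject actually received". Section 7.3.1 says which grouping each disposition table uses; 7.5.1.1 says only treatment group.

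**The concern.** A treated-subjects denominator is common when each cohort's response rate is reported on its own. Here it feeds a between-arm test whose validity comes from randomisation. Because allocation is known before the first dose, failing to start treatment can depend on the arm. The multi-tumour SAP, in its SCLC sample-size paragraph, itself expects more toxicity with the combination. An undosed subject counted in the denominator would be a non-responder, so leaving that subject out can only keep or raise that arm's ORR. If this happens more in one arm, the comparison is shifted by selection after randomisation.

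Section 4.1.1 also does not line up with itself: best response is counted from the date of treatment assignment, but a subject enters the denominator only on receiving a dose. No planned analysis would show a reader how much the exclusion matters.

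**Working it through.** **1. Reproduce the plan's power.** Section 5 gives N = 150 and 100, a two-sided 5% level and "78% power to detect the difference between these two arms", "if the true ORR rates are 10% and 23%, respectively".

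Pooled-variance normal approximation: power = Φ[(d − 1.96·s0)/s1].
- d = 0.23 − 0.10 = 0.13
- pooled rate = (15 + 23)/250 = 0.152
- s0 = √[0.152 × 0.848 × (1/150 + 1/100)] = 0.0464
- s1 = √[0.10 × 0.90/150 + 0.23 × 0.77/100] = 0.0487
- (0.13 − 1.96 × 0.0464)/0.0487 ≈ 0.80, so power = 78.9%

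This agrees with the stated 78%. Other methods lie close: 76.1% with unpooled variance, 76.6% for Fisher's test and 79.8% for the unstratified chi-square test, the last two by exact enumeration.

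**2. Power if all randomised subjects are analysed.** The documents give no untreated share, so a range is assumed. Untreated subjects count as non-responders, so each rate becomes p × (1 − share), with N still 150 and 100.

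| Untreated share (assumed) | Rates | Difference | Power |
|---|---|---|---|
| none | 10.0% / 23.0% | 13.0 points | 78.9% |
| 2% in both arms | 9.8% / 22.5% | 12.7 | 78.0% |
| 5% in both arms | 9.5% / 21.9% | 12.4 | 76.5% |
| 10% in both arms | 9.0% / 20.7% | 11.7 | 74.0% |
| 5% in combination only | 10.0% / 21.9% | 11.9 | 72.6% |
| 10% in combination only | 10.0% / 20.7% | 10.7 | 65.2% |
| 5% in monotherapy only | 9.5% / 23.0% | 13.5 | 82.3% |
| 10% in monotherapy only | 9.0% / 23.0% | 14.0 | 85.4% |

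Balanced non-treatment matters little; imbalance moves the comparison in either direction.

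**3. Effect on the test result.** The stratum counts are unknown, so an unstratified pooled z-test is used: z = (y/m − x/n)/√[p̄(1 − p̄)(1/n + 1/m)], with x/n for monotherapy and y/m for the combination.

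Worked case, 17/150 vs 20/100: p̄ = 37/250 = 0.148, SE = 0.0458, difference = 0.0867, z = 1.89, p = 0.059.

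| Monotherapy | Combination | p | What it represents |
|---|---|---|---|
| 17/150 | 20/100 | 0.059 | all randomised |
| 17/150 | 20/98 | 0.050 (0.0499) | 2 untreated, combination only |
| 17/150 | 20/95 | 0.038 | 5 untreated, combination only |
| 17/143 | 20/95 | 0.056 | similar untreated share in both arms |
| 17/150 | 19/95 | 0.062 | one responder fewer, treated only |
| 17/150 | 21/100 | 0.037 | one responder more, all randomised |
| 15/150 | 23/100 | 0.005 | planning rates, all randomised |
| 15/150 | 23/95 | 0.003 | planning rates, 5 untreated, combination only |

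The combination's ORR in the 20-responder case is 20/100 = 20.0% on all randomised and 20/95 = 21.1% on treated subjects.

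**4. How often the two analyses would disagree.** Take 10% and 23% as the rates among dosed subjects, with untreated subjects in the combination arm only. Summing binomial probabilities over all outcomes, the two analyses fall on opposite sides of 0.05 in about 2% of trials with 2 untreated and about 5% with 5 untreated.

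**The case against.** The strongest defence is practical. Few randomised subjects may go undosed, and a similar share in each arm changes almost nothing. Treated-subjects ORR is also consistent with how the rest of this trial is reported. That stands as a limit on size. It does not answer why a randomised population was defined and then used in no efficacy analysis.

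Four stronger readings are tempting, and the text does not support them.

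- **The test moves subjects to the arm they actually received.** Section 6.2 defines that grouping but does not tie it to the CMH test. Section 7.3.1 names a grouping where one is meant; 7.5.1.1 does not. The supportable statement is that the grouping is unspecified. Moving a subject would also be rare, since it requires the wrong drug for the whole treatment period.
- **The choice of population reverses the conclusion.** The 0.059 and 0.038 pair is a knife-edge case. It disappears with one combination responder more or fewer, with similar non-treatment in both arms, or at the planning rates.
- **The 78% power is wrong.** It reproduces. Section 5 uses the randomised numbers as denominators, which is no error in the figure.
- **PFS and OS should start at randomisation.** In the readable text these are per-arm Kaplan-Meier estimates from first dose with no between-arm test, so the problem described here does not require that change. The never-treated category in the PFS censoring table of 7.5.2.1 sits oddly with a first-dose origin, but that is a wording matter.

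**Conclusion.** The point holds for the primary ORR comparison. Its treated-subjects denominator permits selection after randomisation in an open-label trial, its grouping rule is not stated, and no ORR sensitivity analysis on the randomised population would expose the effect.

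The likely size is small. A changed conclusion needs a borderline result together with uneven non-treatment. This rests on assumed untreated counts (2 or 5 of 100) or shares (2% to 10%), unstratified calculations, and untreated subjects counted as non-responders. It should be corrected because the randomised analysis is the one the design supports and the population already exists. It does not show that the planned result would be wrong.

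**What to change.** In 4.1.1, 7.1 and 7.5.1.1 of the SCLC expansion SAP:

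1. State that the primary CMH test, odds ratio and ORR difference use All Randomized Subjects, grouped as assigned by IVRS.
2. Count untreated or unassessed subjects as non-responders.
3. Keep the all-treated analysis as a sensitivity analysis in 7.5.1.2 and state its grouping.

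If the sponsor prefers to keep the treated set as primary, the minimum is to state the grouping and add the all-randomised analysis as a sensitivity analysis.

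**Cost.** A few sentences and one rerun of the ORR tables on a population already defined. ORRs become slightly lower. By the same approximation, power falls from 78.9% to 78.0% with 2% untreated in both arms, to 76.5% with 5% in both arms, and to 72.6% with 5% in the combination arm only.

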### 4.2 Secondary

The secondary objective (to assess the safety and tolerability of nivolumab monotherapy or nivolumab combined with ipilimumab in subjects with advanced or metastatic SCLC) will be

primarily assessed by the rate of treatment-related AEs leading to drug discontinuations during the first 12 weeks of treatment. In addition, safety and tolerability will be analyzed through the incidence of adverse events, serious adverse events, and specific laboratory abnormalities (worst grade). Toxicities will be graded using the National Cancer Institute (NCI) Common Terminology Criteria for Adverse Events (CTCAE) version 4.0.

ORR will be further characterized by the duration of response (DOR) and the magnitude of reduction in tumor volume. DOR will be computed for subjects with a BOR of PR or CR and is defined as the time from first confirmed response (CR or PR) to the date of the first documented tumor progression as determined using RECIST 1.1 criteria or death due to any cause, whichever occurs first. For subjects who neither progress nor die, the DOR will be censored on the date of their last evaluable tumor assessment. Subjects who start subsequent therapy without a prior reported progression will be censored at the last evaluable tumor assessment prior to initiation of the subsequent anticancer therapy. The magnitude of reduction in tumor volume is defined as the percent decrease in tumor volume from baseline to nadir, observed before the time of the first documented tumor progression or death.

Progression free survival (PFS) is defined as the time from first dosing date to the date of the first documented progression, as determined by the investigator or BICR (per RECIST 1.1), or death due to any cause, whichever occurs first. Subjects who die without a reported progression or start of any subsequent anti-cancer therapy will be considered to have progressed on the date of their death. Subjects who did not progress or die will be considered as not progressed and will be censored on the date of their last evaluable assessment or last evaluable assessment prior to crossover. Subjects who did not have any on study assessments and did not die will be censored on the first dosing date. Subjects who started any subsequent anti-cancer therapy without a prior reported progression will be censored at the last evaluable assessment prior to initiation of the subsequent anti-cancer therapy. Please refer to Table 4.2-1 for the censoring scheme in primary analysis of PFS.

**Table 4.2-1: Censoring scheme used in primary analysis of PFS**

Situation	Date of Progression or Censoring	Outcome
No baseline tumor assessments and no death	First dosing date	Not Progressed
No on study tumor assessments and no death	First dosing date	Not Progressed
Progression documented between scheduled visits	Date of the first documented tumor progression per RECIST 1.1	Progressed
Clinical progression without evidence of progression per RECIST 1.1 or No progression	Date of last tumor assessment with no documented progression or last evaluable assessment prior to crossover (for crossover subject without PD)	Not Progressed

**Table 4.2-1: Censoring scheme used in primary analysis of PFS**

Situation	Date of Progression or Censoring	Outcome
New anticancer treatment started without a prior reported progression	Date of last tumor assessment prior or on the date of initiation of the subsequent anti-cancer therapy	Not Progressed
Death without progression per RECIST 1.1	Date of death	Progressed

OS is defined as the time between the first dosing date and the date of death due to any cause. A subject who has not died will be censored at the last known alive date. OS will be followed continuously while subjects are on the study drug and every 3 months via in-person or phone contact after subjects discontinue the study drug.

[Redacted text block]

[REDACTED]

[REDACTED]

[REDACTED]

[REDACTED]

[REDACTED]

[REDACTED]

[REDACTED]

[REDACTED]

[REDACTED]

[REDACTED]

## 5 SAMPLE SIZE AND POWER

### Sample size determination for SCLC expansion cohort

In Amendment 09, in addition to the original two-stage design of SCLC subjects, additional SCLC expansion cohort subjects will be randomized in a 3:2 ratio to one of 2 expansion groups: Arm A (150 subjects, nivolumab mono) or Arm B (100 subjects, nivolumab 1 mg/kg + ipilimumab 3 mg/kg) and will be stratified for number of prior treatment lines (1 vs 2 prior chemotherapy regimens).

Based on SCLC data so far observed in this study with an ORR of about 10% for nivolumab monotherapy and about 23% for nivolumab / ipilimumab combination therapy, sample sizes of  $N = 150$  for nivolumab monotherapy and  $N = 100$  for nivolumab / ipilimumab combination therapy (nivolumab 1 mg/kg + ipilimumab 3 mg/kg) will target a Type I error rate of 5% (two-sided) and will have 78% power to detect the difference between these two arms, if the true ORR rates are 10% and 23%, respectively.

